2 BACKGROUND AND RATIONALE

2.1 Background

Neurofibrillary tangles begin during the preclinical phase of AD, and by the time of very mild dementia neurofibrillary tangles are well formed in predictable staged patterns (Braak & Braak, 1990; Braak et al., 1993). However, the rate of temporal change in neurofibrillary tangle burden in individual cases is poorly understood. Until recently, the information about the temporal and spatial signal from neurofibrillary tangle (tau related) pathology in AD has come from neuropathology studies of brain bank cases (Gomez-Isla et al., 1996) and in life from CSF tau protein levels which have no spatial information and suffer from lack of standardized assays from lab to lab (Mattsson et al., 2013). The advent of tau positron emission tomography (PET) imaging using compounds (Chien et al., 2014; Maruyama et al., 2013; Villemagne et al., 2014) such as [F-18]AV1451 and now [F-18]MK6240 (Hostetler et al., 2016; Lohith et al., 2018) hold promise of making major breakthroughs in diagnosing AD accurately and characterizing its rate of progression.

[¹⁸F]MK-6240 has been previously evaluated by several groups including ours (Betthausen et al., 2018) demonstrating substantial NFT deposition in the AD subjects and no or little evidence for tau binding in the HV subjects in the absence of amyloid. This study aims to evaluate the longitudinal change in tau burden using [¹⁸F]MK-6240 PET imaging in relation to cognitive and functional metrics.

3 STUDY OBJECTIVES

3.1 Primary Objective

The primary objectives of this study is:

- To estimate rates of longitudinal change in [¹⁸F]MK-6240 brain uptake at 26 and 52 weeks compared to baseline in subjects with dementia due to AD, mild cognitive impairment (MCI) and healthy volunteers (HV).
- To correlate the changes in [¹⁸F]MK-6240 uptake and changes in clinical cognitive assessments (MMSE, ADAS-cog and CDR).

3.2 Secondary Objectives

The secondary objectives of this study are:

- To estimate rates of longitudinal change in [¹⁸F]MK-6240 brain uptake at 104 (24 months) weeks compared to baseline in subjects with dementia due to AD, mild cognitive impairment and healthy volunteers.
- To evaluate cross-sectional comparison of [¹⁸F]MK-6240 uptake in AD, MCI and HV at baseline 26, 52 and 104 weeks

4 STUDY DESIGN

This is a longitudinal, observational study evaluating the imaging characteristics of the tau PET radioligand [¹⁸F]MK-6240 in AD, MCI and HV subjects. Up to 28 MCI/mild AD subjects, up to 5

moderate AD subjects, and up to 9 similarly aged HV subjects will be enrolled at the University of Wisconsin-Madison. Recruitment as well as screening and longitudinal clinical activities, including MRI, [¹¹C]PiB and [¹⁸F]MK-6240 PET imaging, will be completed. The general design of the study is provided in **Table 1**.

5 STATISTICAL ANALYSIS PLAN

5.1 Image Pre-processing

The MRI, PiB and [¹⁸F]MK-6240 PET images will be co-registered for anatomy-based definition of regions of interest (ROI) for analysis of regional [¹⁸F]MK-6240 binding/uptake. The PET analyses will include application of spatially standardized region of interest (ROI) templates to assess tracer uptake and quantification. Standardized Uptake Value Ratios (SUVR) will be calculated as described by Betthausen et al 2018 and ROIs extracted that represent Braak and Braak staging.

Tau Braak and Braak stage equivalent regions of interest using the Harvard Oxford Brain atlas for defining regions of interest bilaterally:

Stage I: entorhinal cortex average SUVR

Stage II: Hippocampus and amygdala average SUVR

Stage III: fusiform average SUVR

Stage IV: Inferior temporal and middle temporal gyrus average SUVR

Stage V: Superior temporal gyrus average SUVR

Stage VI: Cuneus and pericalcarine cortex average SUVR

Amyloid load:

PIB Index: is comprised of the average signal extracted from the DVR image of eight bilateral ROIs including the anterior cingulate, posterior cingulate, precuneus, angular gyrus, supramarginal gyrus, superior temporal gyrus, middle temporal gyrus, medial orbital gyrus.

Visual rating: As described in Johnson et al 2014 a rating of elevated, not elevated or indeterminate is assessed for each amyloid scan.

MRI:

Hippocampal volume: obtained using FIRST/FSL and adjusted for total intracranial volume using a regression approach.

Total atrophy: expressed as a ratio of the volume of segmented CSF to the volume of segmented brain (gray + white matter).

5.2 Descriptive Statistics:

General approach: Because the sample sizes are small, and because the goal of the project is to characterize rates of change by clinical status, the objectives of the analyses are largely descriptive in nature.

The demographic and baseline characteristics will be summarized according to the clinical group (HV, MCI, mild or moderate AD) using descriptive statistics for continuous variables and using frequency count and percentage for discrete variables. Plots of relevant variables will be examined for skewness and transformed as necessary prior to any analyses.

Descriptive statistics and counts (with histograms when relevant) will be ascertained for the following variables by diagnostic group:

Age, sex, education, race/ethnicity; ADAS-Cog total score and ADAS-Cog13 subscore, MMSE score; CDR-sum and weighted scores; Amyloid status and PIB index score; MK6240 estimated Braak stage and SUVR values for each of six regions of interest representing each Braak Stage; hippocampal volume (corrected for total intracranial volume) and estimate whole brain atrophy (CSF volume to brain volume).

The Baseline [¹⁸F]MK-6240 binding will be compared among the AD subjects at different stages of the disease, and HV groups descriptively, quantitatively and visually by graphical plots. A primary region of interest will be comprised of the average signal in the entorhinal cortex, amygdala, hippocampus, and anterior fusiform gyrus [¹⁸F]MK-6240 binding in AD at different stages of the disease, and HV binding across multiple regions will be compared. Within the AD groups, the distribution and binding of [¹¹C]PiB will be compared to the [¹⁸F]MK-6240 binding across multiple regions.

Cross-sectional Spearman correlations will be computed by group at Baseline, 6, 12 and 24 months for the following measures: [¹⁸F]MK-6240 uptake neuropsychological testing (MMSE, CDR-SB, ADAS-cog), hippocampal volume and whole brain atrophy.

5.3 Longitudinal Analysis

The primary objective of this imaging trial is to evaluate the longitudinal change in [¹⁸F]MK-6240. Composite and regional SUVRs will be determined for each of the [¹⁸F]MK-6240 imaging sessions (Baseline, 6-month, 12-month, and 24-month) in the six specific regions (approximating Braak stages) as described above. Change in tau regional deposition as measured by [¹⁸F]MK-6240 will be determined by estimating the mean change from baseline to each follow-up visit for each ROI by diagnostic group. The mean change and standard deviation will be computed for each region and group. These regional means and SDs by region and group are the primary objectives of the project. The Kruskal-Wallis test will be performed to determine if rates of change differ by group.

The relationship between the change in tau deposition by [¹⁸F]MK-6240 and baseline PIB status will be assessed with Spearman correlation.

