3 STUDY PURPOSE

The overall goal of this study is to evaluate the longitudinal change in the uptake of [¹⁸F]MK-6240. The data obtained will be vital in forming hypotheses for future larger studies, particularly for hypotheses about effect sizes that may inform future large scale clinical trials.

4 **STUDY OBJECTIVES**

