10.3 Statistical Analysis

Descriptive statistics will be used to describe the tau deposition (e.g. composite and regional SUVR, voxel based statistics or change in tau distribution) using [¹⁸F]MK-6240 PET.

The Baseline [¹⁸F]MK-6240 binding will be compared among the AD subjects at different stages of the disease, and HV groups descriptively, quantitatively and visually by graphical plots. [¹⁸F]MK-6240 binding in AD at different stages of the disease, and HV binding across multiple regions will be compared. Within the AD groups, the distribution and binding of [¹¹C]PiB will be compared to the [¹⁸F]MK-6240 binding across multiple regions.

The primary objective of this imaging trial is to evaluate the longitudinal change in [¹⁸F]MK-6240. Composite and regional SUVRs will be determined for each of the [¹⁸F]MK-6240 imaging sessions (Baseline, 6-month, 12-month, and 24-month). This may also include 78 (18 month) and/or 130 (30 month) week measures, if the 26, 52, or 104 week measures are not available in order to assess change over intervals of 6, 12, 18 and 24 months. The analysis will include, but not be limited to, the following regions of interest: inferolateral temporal cortex, posterior cingulate, frontal cortex, parietal cortex, occipital cortex, mesial temporal cortex and anterior cingulate. To help control type 1, a composite inferomedial region will be used as the primary outcome. Change in tau regional deposition and/or volume of deposition as measured by [¹⁸F]MK-6240 (e.g. composite and regional SUVR, voxel based statistics or change in tau distribution) will be determined by estimating the change from baseline to each follow-up visit using an appropriate repeated measures metric. The change in tau burden will be compared among the groups (HV, prodromal, mild and moderate AD).

The relationship between the change in tau deposition by [¹⁸F]MK-6240 (e.g. composite and regional SUVR, voxel based statistics or change in tau distribution) and change in clinical

biomarker measures will be examined in prodromal, mild and moderate AD subjects. In addition, the correlation between baseline tau burden and AD severity based on clinical scales, venous blood biomarkers in prodromal, mild and moderate AD subjects will be evaluated.

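### SAP 5.3 reports only separate baseline-to-visit changes; no planned analysis pools a subject's scans into the rate the SAP sets out to estimate, or estimates scan noise and slope variation directly

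*SAP*

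**What the plan says.** Protocol 10.3 describes the longitudinal analysis as "estimating the change from baseline to each follow-up visit using an appropriate repeated measures metric". It names no model.

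SAP 5.3 keeps the target but not the repeated-measures wording: change "will be determined by estimating the mean change from baseline to each follow-up visit for each ROI by diagnostic group". It continues: "The mean change and standard deviation will be computed for each region and group". It then gives these figures the highest status: "These regional means and SDs by region and group are the primary objectives of the project". The between-group comparison is also worded in terms of rates: "The Kruskal-Wallis test will be performed to determine if rates of change differ by group".

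SAP 3.1 opens its first primary objective with "To estimate rates of longitudinal change in" tracer uptake. SAP 5.5 makes the 12-month change in a composite region the primary endpoint, and the 6- and 24-month changes secondary. Protocol section 3 states the use of the results: "hypotheses about effect sizes that may inform future large scale clinical trials".

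SAP 5.4 bases the sample size on practical considerations, with floors of 15 MCI/mild AD, 3 moderate AD and 5 healthy volunteers who have at least the 12-month scan. Up to 28, 5 and 9 may enrol. SAP 5.6 says that imputation will be used and that missingness is taken to be not random, without naming a method.

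**The concern.** The SAP speaks of rates, but nothing in 5.3 computes one. Each visit is compared with baseline on its own and no model links one person's scans. A subject seen at baseline and 6 months informs one table, a subject with all four scans informs three, and the tables are never combined.

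Two things are at stake, both tied to planning later trials. The first is precision: groups are small and the plan expects losses, since up to 42 people may have a baseline scan so that at least 23 finish. The second is the meaning of the SD. The SD of a single difference mixes true variation in rate with measurement noise from two scans. A planner with a different trial length or scan schedule needs the two parts separately, and the SAP does not plan to estimate either directly.

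**Working it through.** **Inputs.** Scan times of 0, 0.5, 1 and 2 years (SAP 5.3). Group sizes from SAP sections 4 and 5.4. The plan states no SD, effect size or power, so there is no figure to reproduce. Assumed model: SUVR = subject intercept + subject slope × years + scan noise, with slope SD τ per year, noise SD s, and k = s/τ. Because k is not given, a range of 0.25 to 1 is shown. Variances below are in units of τ².

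**Variance of the yearly rate per subject**

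- 12-month change: 1 + 2k².
- 24-month change divided by 2: (4 + 2k²)/4 = 1 + 0.5k².
- Least-squares slope over all four scans: mean time 0.875, Sxx = 2.1875, so 1 + k²/2.1875 = 1 + 0.457k².
- Scans at 0, 6 and 12 months: Sxx = 0.5, so 1 + 2k². This equals the 12-month change, because the middle scan has zero weight.
- Scans at 0 and 6 months: Sxx = 0.125, so 1 + 8k².

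**Subjects with all four scans**

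| k | 12-month | 24-month ÷ 2 | four-scan slope | 12-month excess | 24-month excess |
|---|---|---|---|---|---|
| 0.25 | 1.125 | 1.031 | 1.029 | 9% | 0.3% |
| 0.5 | 1.500 | 1.125 | 1.114 | 35% | 1% |
| 1 | 3.000 | 1.500 | 1.457 | 106% | 3% |

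The gain over the 12-month change comes from the 24-month scan, and the planned 24-month endpoint already captures nearly all of it.

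**With attrition.** Take the 28 MCI/mild AD subjects the plan allows, of whom 15 have all scans. Assume that 7 stop after 12 months and 6 after 6 months. The 12-month analysis then has 15 + 7 = 22 subjects and the 24-month analysis has 15, before any imputation. A pooled slope weights each subject by inverse variance:

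information = 15/(1 + 0.457k²) + 7/(1 + 2k²) + 6/(1 + 8k²)

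- k = 0.25: 14.58 + 6.22 + 4.00 = 24.81, variance 0.0403. The 12-month analysis gives 1.125/22 = 0.0511 and the 24-month 1.031/15 = 0.0688. Reductions: 21% and 41%.
- k = 0.5: 13.46 + 4.67 + 2.00 = 20.13, variance 0.0497, against 0.0682 and 0.0750. Reductions: 27% and 34%.
- k = 1: 10.29 + 2.33 + 0.67 = 13.29, variance 0.0752, against 0.1364 and 0.1000. Reductions: 45% and 25%.

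**What the SDs contain.** Under the same model, Var(12-month change) = τ² + 2s² and Var(24-month change) = 4τ² + 2s². Noise makes up 2k²/(1 + 2k²) of the first: 11%, 33% and 67% at k = 0.25, 0.5 and 1.

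**The case against.** **The protocol does not promise a slope.** Its target is also change to each visit. In a check on simulated complete data, a mixed model with visit as a category returned exactly the simple 12-month mean change. A reader might infer that the dropped phrase is why two of a complete subject's four scans do not enter the 12-month estimate. That is not so, and restoring the phrase alone would change nothing for those subjects. This part of the objection stands: the SAP has to name a model that links the visits.

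**The planned outputs already hold much of the information.** For complete subjects the 24-month change nearly matches the slope. The visit SDs also allow a split: τ² = (Var24 − Var12)/3 and 2s² = (4Var12 − Var24)/3, which gives an 18-month variance of Var12 + (1.25/3)(Var24 − Var12). It is therefore too strong to say that the 12-month SD cannot be carried to a trial of another length. What remains is that this is a crude difference of two small-sample variances, taken from different sets of subjects once there is dropout.

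**Early leavers.** A reader might infer that someone who leaves before month 12 contributes nothing to the 12-month figure. SAP 5.6 plans imputation, which could use the 6-month scan, and such subjects may be replaced. But the method is unnamed, so how much is recovered cannot be judged.

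**Linearity.** A slope over 24 months is not the 12-month change if the course bends. With a term c·t², the four-scan slope differs from the 12-month change by 1.07c. This is a sound reason not to replace the declared endpoint.

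**Simple summaries suit small samples,** as SAP 5.2 says. They do, but the same section gives the goal as characterising rates of change, and a pooled slope serves that goal.

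**Conclusion.** The gap is real and worth closing, but moderate. The SAP sets out to estimate rates for trial planning, and no planned analysis pools a subject's scans into a rate or estimates slope SD and residual SD directly.

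The 9% to 106% figure applies only against the 12-month change and should not be read as what a mixed model adds to the whole plan. For complete subjects, the addition over the 24-month change is at most 3% across the range shown. The firmer argument is attrition, where pooling gains on both planned outputs. Those figures rest on the assumed k, linear change, the assumed dropout pattern, and no recovery through imputation.

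Nor do the documents support saying that every group has 15 or fewer patients: 15 is a floor for MCI and mild AD combined, and up to 28 may enrol. The moderate AD and healthy groups are small on any reading (at most 5 and 9), so their slope SDs will be imprecise under any method.

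**What to change.** Keep the 12-month change as the primary endpoint and keep the visit-wise means and SDs. Add to SAP 5.3 a linear mixed model with group, years since the baseline scan and their interaction, a random intercept and slope, and a residual variance shared across groups, fitted to all analysable scans. Report each group's slope with a confidence interval, the between-subject slope SD and the residual SD, and name these as the planning quantities.

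Leave the Kruskal-Wallis test on the visit-wise change. Alternatively, apply it to annualised slopes, but only in subjects with a scan at 12 months or later. A slope from scans at 0 and 6 months carries noise variance 8s², against 0.457s² from four scans, and the ranks would treat the two alike.

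The cost is a paragraph in the SAP and a few lines of R, with no new data. The model assumes roughly linear change, to be checked against the visit-wise means. It also assumes data missing at random, so the not-random assumption in SAP 5.6 should become a stated sensitivity analysis.

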STUDY DESIGN	
This is a longitudinal, observational study evaluating the imaging characteristics of the tau PET radioligand [¹⁸F]MK-6240 in AD, MCI and HV subjects. Up to 42 subjects including approximately 28 MCI/mild AD subjects, up to 5 moderate AD subjects, and 9 similarly aged HV subjects will be consented and screened. Imaging procedures include [¹¹C]PiB, [¹⁸F]MK-6240 PET and structural MRI.
 
All subjects who complete at least one [¹⁸F]MK-6240 PET imaging session will be considered enrolled in the study. As many as 28 MCI/mild AD subjects, 5 moderate AD subjects, and 9 similarly aged HV subjects may complete an evaluable baseline [¹⁸F]MK-6240 PET scan to enable at least 23 subjects (14 MCI/mild AD, 3 moderate AD, 6 HV subjects) to complete the 24 month follow up. Subjects who discontinue prior to completing the 12-month [¹⁸F]MK-6240 PET scan may be replaced in the study until a total of 15 patients (MCI/AD) complete the 12 month PET imaging session. Subjects that complete the 12-month visit but wish to abandon the study before the 24-month visit will be given the option to have a final evaluation any time between 18 and 24 months.
 
All subjects (or their legal authorized representative when applicable) will provide informed consent before any study procedures are performed. The Screening procedures will occur within 60 days prior to baseline [¹⁸F]MK-6240 imaging and will include a brief cognitive assessment, review of medical history and medications, physical examination, [¹¹C]PiB PET imaging and brain MRI.

--------------	---

[¹¹C]PiB and MRI IMAGING:

As part of the Screening Visit, subjects will complete structural brain MRI imaging which will be used for eligibility evaluation, co-registration with PET imaging and volumetric analysis.

If an evaluable PiB scan has been acquired and is available for use in this study and occurred within 12 months of screening, the scan will not be repeated. Otherwise, [¹¹C]PiB PET imaging will be obtained at screening to evaluate for amyloid deposition. Subjects will be considered amyloid positive if [¹¹C]PiB DVR (distribution volume ratio) imaging demonstrates amyloid deposition based on qualitative read or DVR index value >1.20.

For the [¹¹C]PiB PET imaging session, subjects will receive a single IV bolus injection target dose of 15 mCi ± 20% of [¹¹C]PiB and scanned dynamically for 70 minutes.

[¹⁸F]MK-6240 PET IMAGING VISITS:

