Inclusion Criteria for Healthy Volunteer Subjects (HV)

- Normal Cognition based on cognitive results at screening.
- Healthy with no clinically relevant finding on physical examination at screening and upon reporting for the Baseline [¹⁸F]MK-6240 imaging visit.
- CDR global score =0

Inclusion Criteria for Subjects with a Diagnosis of MCI or Dementia Due to AD

- Have screening [¹¹C]PiB PET imaging demonstrating amyloid binding based on qualitative read or DVR index value >1.20.
- MMSE score 26-30 (inclusive), CDR global score 0.5 for subjects with MCI
- MMSE score 22-26 (inclusive), CDR global score 0.5 or 1 for subjects with mild dementia due to AD
- MMSE score 16-21 (inclusive), CDR global score 1-2 for subjects with moderate dementia due to AD
- Subjects with MCI must meet 2018 research criteria for MCI (Jack et al., 2018).
- Subjects with dementia must meet 2018 research criteria for dementia (Jack et al., 2018).
- A structural brain MRI with no evidence of non-AD disease to account for dementia or MRI exclusion criteria.

Exclusion Criteria (for all subjects)

- Subject has received an investigational drug or device within 30 days of screening.
- For women, pregnant, lactating or breastfeeding or intention to become pregnant.
- Evidence of unstable or untreated clinically significant gastrointestinal, cardiovascular, hepatic, renal, hematological, neoplastic, endocrine, alternative neurological, immunodeficiency, pulmonary, or other disorder or disease. Stable, treated chronic medical conditions like hypertension, hypercholesterolemia, diabetes mellitus, non-metastatic dermatologic or prostatic cancer, etc. are acceptable as long as they do not, in the study investigator's opinion, contribute to cognitive dysfunction or limit participation in study procedures.
- Any illness or other consideration that makes it unlikely that the subject will be able to complete the 24-month study.
- Current or prior history (within past 5 years) of significant alcohol or substance abuse as determined by the investigator.
- Psychiatric disorders that may interfere with the study including current major Axis I DSM-V disorders including but not limited to severe Major depression, current or history of bipolar I disorder, or schizophrenia.
- Non-English speakers or subjects who are unable to comprehend study materials are excluded at entry

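### SAP 5.3 correlates tau change with an undefined PIB status; if this means amyloid positivity, it is constant in all MCI/AD patients, and a pooled coefficient is confounded with diagnosis

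*SAP*

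**What the plan says.** SAP 5.3 (Longitudinal Analysis) closes by saying that the relation between change in [18F]MK-6240 and "baseline PIB status will be assessed with Spearman correlation". The sentence does not define or code PIB status, and it does not say whether the correlation is by group or pooled. SAP 5.2 does specify by-group computation for its own cross-sectional Spearman correlations.

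Three amyloid variables in the SAP could be meant:

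- **Positivity rule.** The SAP synopsis counts a subject as amyloid positive if "imaging demonstrates amyloid deposition based on qualitative read or DVR index value >1.20".
- **Visual rating.** SAP 5.1 says that "a rating of elevated, not elevated or indeterminate is assessed for each amyloid scan".
- **PIB Index.** SAP 5.1 says that it "is comprised of the average signal extracted from the DVR image of eight bilateral ROIs". It is continuous.

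SAP 5.1 calls neither of its two measures a status. The list of variables in SAP 5.2 names amyloid status and the PIB index score as separate items.

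On eligibility, the synopsis requires every MCI or AD patient to have screening "imaging demonstrating amyloid binding based on qualitative read or DVR index value >1.20", which is the positivity rule again. Volunteers must show "Normal Cognition based on cognitive results at screening", an unremarkable physical examination and a CDR global score of 0. They have no amyloid criterion.

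**The concern.** Taken as positivity, status separates nobody among the patients, because they were selected on it. The correlation could then say nothing about whether more amyloid goes with faster tau accumulation in MCI or AD. A pooled coefficient could still be computed if some volunteers are PiB-negative, but it would largely restate that patients and volunteers differ, a comparison that the Kruskal-Wallis test in the same section already makes. Reported as an amyloid-tau relationship, it could mislead those who use these data to plan later trials. The SAP says the R scripts will be shared with sponsors, and a programmer cannot tell from the text which variable or analysis set to use.

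**Working it through.** The plan states no coefficient, power or alpha for this analysis, so there is no figure of its own to reproduce.

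**Inputs from the documents.** The minimum with a 12-month scan is 15 MCI/mild AD + 3 moderate AD + 5 volunteers (SAP 5.4), which is 18 patients and 5 volunteers, n = 23. The maximum is 28 + 5 + 9 (SAP synopsis), which is 33 patients and 9 volunteers, n = 42.

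**Assumptions.** The number k of PiB-negative volunteers is not planned, so it is varied. Patient-volunteer differences in tau change of 0.5 and 1 SD are assumed. Simulated data are normal with unit SD within group and no amyloid effect inside either group, with 20,000 trials per scenario for the p<0.05 rates.

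**Step 1: within patients, status as positivity.** Barring eligibility deviations, every patient has status = 1. A constant has zero rank variance, so Spearman's rho is 0/0. The software returns no value at n = 18 or n = 33.

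**Step 2: pooled, status as positivity.** All variation in status comes from the k negative volunteers. With p = k/n, the largest attainable rho is about √(3p(1−p)). For k = 5 and n = 23, p = 0.217 and √(3 × 0.217 × 0.783) = 0.71. At 18 + 5:

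| k negative | Maximum rho | Correlation of status with diagnosis | p<0.05 at 0.5 SD | p<0.05 at 1 SD |
|---|---|---|---|---|
| 0 | undefined | undefined | – | – |
| 1 | 0.35 | 0.40 | 0% | 0% |
| 2 | 0.49 | 0.59 | 8% | 15% |
| 3 | 0.58 | 0.73 | 9% | 23% |
| 4 | 0.66 | 0.87 | 13% | 35% |
| 5 | 0.71 | 1.00 | 14% | 43% |

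At 1 SD the mean rho is about 0.15, 0.28 and 0.38 for k = 1, 3 and 5. At 33 + 9 with all nine volunteers negative, p<0.05 occurs in 24% (0.5 SD) and about 70% (1 SD). Simulation error is about one percentage point.

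**Step 3: all volunteers negative.** Status is then identical to patient versus volunteer, and (n−1) × rho² equals the two-group Kruskal-Wallis statistic. In one simulated data set rho = 0.270, and 22 × 0.270² = 1.61, which matches H = 1.606. The coefficient carries the same information as the collapsed group test.

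**Step 4: pooled, status as the PIB Index.** The variable is no longer constant. If patients' index is assumed to be 2 SD above volunteers', still with no relation inside either group, p<0.05 occurs in 8% (18 + 5) and 11% (33 + 9) at a 0.5 SD difference in tau change, and in 17% and 29% at 1 SD. Naming the index is therefore not enough if groups are pooled.

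**Step 5: precision of the index within patients.** The 95% half-width around zero is tanh(1.96 × √(1.06/(n−3))).

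- n = 18: tanh(1.96 × 0.266) = 0.48
- n = 33: tanh(1.96 × 0.188) = 0.35

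**The case against.** The strongest reply is that the authors meant the continuous index. SAP 5.1 attaches the PIB label to the index, SAP 5.2 uses the different term amyloid status for the categorical item, and a rank correlation suits a graded variable. This may be right, but SAP 5.2 also lists status apart from the index, so the text supports either reading and settles neither. The visual rating could also have been meant. It need not be constant, since a patient can enter on the DVR value alone, but the SAP does not say how an indeterminate read would be ranked.

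A second reply is that pooling is not stated. That is true: the surrounding analyses are by group, and silence does not establish pooling. But a by-group analysis of positivity is undefined in every patient group, so on that reading neither choice informs about patients.

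Third, SAP 5.2 says that "the objectives of the analyses are largely descriptive in nature", and no test or alpha is set for this correlation. That stands. The p<0.05 rates above only gauge how strongly diagnosis alone can drive the coefficient.

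Fourth, a positive-versus-negative contrast may have been the aim. SAP 2.1 reports "no or little evidence for tau binding in the HV subjects in the absence of amyloid". That is a fair question, but only volunteers can answer it without mixing in diagnosis.

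A reader might also infer that an index correlation within patients must be adjusted for clinical stage. If PiB and tau change each rose 1 SD per stage, ignoring stage would give p<0.05 in 30% (stage split 8/7/3) or 49% (14/14/5) with no within-stage relation. The documents do not support that premise: section 2 of the protocol contrasts amyloid with tangles, whose density follows cognitive impairment. With PiB flat across stages the rate is 5%, and with a rise of 0.25 SD per stage it is 7 to 9%. Adjustment is reasonable as a sensitivity analysis but is not required.

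**Conclusion.** The concern holds as a conditional one. What is certain is that SAP 5.3 leaves both the amyloid variable and the analysis set undefined. If status means positivity, the correlation is undefined within patients, and pooled it is confounded with diagnosis to a degree set by the unknown number of PiB-negative volunteers. If the index or the visual rating was meant, constancy need not hold, but pooling would still mix amyloid with diagnosis. The sizes rest on assumed group differences and would change with them; the constancy within patients rests only on the entry criterion being met.

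Two stronger conclusions that a reader might draw are not supported. The planned correlation is not bound to fail, because two of the three readings can be computed in patients. Nor does a pooled coefficient rest on the volunteers alone: the PiB-negative volunteers supply all the variation in status, but their tau change is contrasted with that of every PiB-positive subject.

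The point is minor. This correlation is not among the objectives in SAP 3.1 and 3.2 or the endpoints in SAP 5.5, and the PIB index is described by group in any case.

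**What to change.** Replace the sentence in SAP 5.3 with:

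> The relationship between change in [18F]MK-6240 and the baseline PIB Index (5.1) will be estimated by Spearman correlation within the MCI/AD patients, with a 95% CI and a plot marked by clinical stage. Volunteers will be shown separately, and no coefficient pooled over patients and volunteers will be interpreted as an amyloid-tau relationship.

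A stage-adjusted (partial rank) correlation may be added as a sensitivity analysis. If a positive-versus-negative contrast was intended, define PIB status and describe the contrast among the volunteers only, the one group in which positivity can vary.

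The cost is a few SAP sentences and a few lines of R. The index is already defined, and SAP 5.2 already plans to compare PiB with [18F]MK-6240 within the AD groups. The drawbacks are a restricted PiB range among patients selected as amyloid positive and the wide intervals shown above, so the result should be reported as an estimate and not as a test.
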